13.12.2. Handling of Missing Data

In order to identify each type of missing data, outcome scales will be coded for every patient and visit according to the following scheme (see also Bagiella, 2010):

1 = valid (complete task)

2 = unable to complete (TBI-related neurological reason) [describe reason]

3 = not completed (different reasons, not TBI related) [describe reason]

Date: 040418

STUDY ID: CAPTAIN - rTMS

13.12.3. Worst Rank Imputation

For outcome scales with code "2" a worst rank imputation will be introduced for the corresponding patients since these data are informatively missing (missing not at random, MNAR). These missing data are replaced by the worst possible score of the corresponding outcome scale.

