13.4.2. Defined Efficacy Ensemble

The following ensemble of appropriate single efficacy criteria shall be tested by a multivariate, directional test approach, reflecting the global status of patients in TBI after 3 and 6 months:

Multivariate Efficacy Ensemble

- 1. Processing Speed Index, Changes from Baseline, LPCF, ITT
- 2. Stroop Color-Word Test, Changes from Baseline, LPCF, ITT
- 3. Trail Making Test, Changes from Baseline, LPCF, ITT
- 4. Digit Span, Changes from Baseline, LPCF, ITT
- 5. Montreal Cognitive Assessment, Changes from Baseline, LPCF, ITT
- 6. Stockings of Cambridge (CANTAB), Changes from Baseline, LPCF, ITT
- 7. Reaction Time (CANTAB) , Changes from Baseline, LPCF, ITT
- 8. Hamilton Rating Scale for Depression, Changes from Baseline, LPCF, ITT
- 9. Hamilton Anxiety Rating Scale, Changes from Baseline, LPCF, ITT

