13.12. Accounting for missing data

13.12.1. Missing Data Problems – General Considerations for a TBI Study

Missing data are a problem in every data analysis. Of course, there are always missing data of the type 'missing completely at random' (MCAR), which in principle will not bias the results; the analysis procedure should be able to cope with partially missing data of such a type. In many studies this type of data is treated by LOCF replacement (Last Observation Carried Forward) as far as there exist follow-up measurements at previous visits.

In a study like the one planned there might also be informatively missing data (missing not at random, MNAR): participants of the study died or are unable to complete the tests because of brain-related impairment. Neglecting these missing data might introduce bias.

A reasonable policy for minimizing bias in the case of informatively missing data (MNAR) is the replacement of these missing data by assigning the worst possible score, or a score worse than those observed. It should be noted that this strategy is only reasonable if rank-based robust procedures are used for the data analysis.

The worst rank imputation procedure was recommended by Lachin in his seminal paper about the missing data problem for data missing because of mortality when performing an exercise test (Lachin, 1999). This procedure was also used when analyzing nonfatal outcomes in studies where mortality was a problem (Lusben, 2002; McMahon, 2001). Recently a similar procedure has been proposed by the 'Traumatic Brain Injury (TBI) Clinical Trials Network' when designing the COBRIT study (Bagiella, 2010).

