Temkin (2007) included deaths with the worst rank for the significance tests of neuropsychological scales, but excluded deaths for the calculation of descriptive statistics (e.g., mean, SE estimates). Thus, significance tests reflect all patients with estimation of missing data while the descriptive statistics reflect only the actually observed assessments. We prefer not excluding deaths from descriptive statistics, since the study treatment with more deaths would artificially have better neuropsychological scores while a study treatment preventing deaths would be burdened by rather severe scores of survived patients. The use of robust descriptive statistics in this study allows the inclusion of worst rank scores for deaths also in descriptive analysis. This way, confirmatory analyses and descriptive analysis can be based on the same analysis data and contradictory results are avoided.

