12. STATISTICAL METHODOLOGY

12.1. Data Handling

In order to identify each type of missing data, outcome scales will be coded for every patient and visit according to the following scheme (see also Bagiella, 2010):

- 1 = valid (complete task)
- 2 = unable to complete (TBI-related neurological reason) [describe reason]
- 3 = not completed (different reasons, not TBI related) [describe reason]

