12.2. Descriptive Statistics

Descriptive account of all variables (raw and baseline difference)

- Range
- Minimum value
- Maximum value
- Mean (+ Std. error)

Cerebrolysin and repetitive Transcranial Magnetic Stimulation (rTMS) in patients with Traumatic Brain Injury

- Standard Deviation
- Variance
- Skewness (+ Std. error)
- Kurtosis (+ Std. error)

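### Substituting the worst raw score does not guarantee the worst rank when the endpoint is a change from baseline, and the SAP gives no rule for these patients

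*Protocol*

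**What the plan says.** Protocol 13.12.2 assigns each outcome scale a code at every visit, and baseline is not excluded. For code 2, Protocol 13.12.3 says that "a worst rank imputation will be introduced for the corresponding patients since these data are informatively missing", and then gives the operation: "These missing data are replaced by the worst possible score of the corresponding outcome scale".

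The general policy in Protocol 13.12.1 is wider. It allows "assigning the worst possible score, or a score worse than those observed", but 13.12.3 takes up only the first option. Section 13.12.1 also means deaths to be ranked worst, yet the three-code scheme has no code for death.

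The analysed variables are changes. The ensemble in Protocol 13.4.2 runs from "1. Processing Speed Index, Changes from Baseline, LPCF, ITT" through "5. Montreal Cognitive Assessment, Changes from Baseline, LPCF, ITT" to HAM-A, nine components in all. SAP 8.2.1 and 9 repeat the list.

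SAP 12.1 keeps the codes, including "2 = unable to complete (TBI-related neurological reason) [describe reason", but attaches no action to them. On summaries, Protocol 13.12.1 reasons that "The use of robust descriptive statistics in this study allows the inclusion of worst rank scores for deaths also in descriptive analysis". The list in SAP 12.2 (Descriptive Statistics) contains "Mean (+ Std. error", standard deviation, variance, skewness and kurtosis, but no median or quartiles.

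**The concern.** A worst rank on the raw score and a worst rank on the change are different things. If the worst score is put in first and the baseline is then subtracted, the result depends on where the patient started. A patient who was already near the bottom of the scale has little room to fall, so the imputed change is small. A patient untestable at baseline and at follow-up has both values set to the worst score and a change of exactly zero. These patients then rank above completers who got measurably worse.

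Code-2 patients are also not tied. Among them, the one with the poorer baseline receives the better rank.

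The protocol adopted worst ranks to limit bias from informative missingness in its primary analysis. The rule can miss that aim for patients closest to the floor, and it leaves the analyst free to choose the order of operations. The point applies to any rank test on the changes, whether the directional test in Protocol 13.10 or the Kruskal-Wallis and Dunn tests in the SAP.

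**Working it through.** The documents give no figure for the effect of the imputation, so there is none to reproduce. The sample size of 30 per group in Protocol 13.9 does not depend on this rule.

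**Inputs from the documents.** All components are changes from baseline (Protocol 13.4.2). MoCA has a maximum of 30 and HAM-A a range of 0 to 56 (Protocol 9.1). The Mann-Whitney measure (MW) counts ties as one half (Protocol 13.10).

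**Assumptions.** The worst MoCA score is 0. Completers' MoCA changes are normal with mean +2 and SD 3.

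**Step 1: the imputed change.** Where higher is better and the worst score is 0, a code-2 patient with baseline b gets 0 − b = −b. If baseline is also code 2, the change is 0 − 0 = 0. This step is algebra and needs no distributional assumption.

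**Step 2: completers outranked.** The share is q = Φ((−b − mean)/SD).

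| b | q at mean +2 | q for mean +3 to +1 |
|---|---|---|
| 0 | Φ(−0.667) = 25.2% | 16% to 37% |
| 2 | Φ(−1.333) = 9.1% | 5% to 16% |
| 4 | Φ(−2.000) = 2.3% | 1% to 5% |
| 6 | Φ(−2.667) = 0.4% | 0.1% to 1% |

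A simulation with whole-point changes, counting only completers strictly outranked, gives 20% at b = 0 and 6.7% at b = 2. Adding half the ties brings these back to about 25% and 9%. Over a wider range (mean 0 to +4, SD 2 to 4) the strict shares are 1% to 45% at b = 0, 0.05% to 27% at b = 2, 0% to 5% at b = 6, and under 0.5% at b = 10.

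**Step 3: HAM-A.** Higher is worse, so the imputed change is 56 − b. A baseline of 15 gives +41 and a baseline of 25 gives +31. Both are effectively the worst rank.

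**Step 4: effect on one component.** Suppose 10% of controls and no test patients are code 2, and completers do not differ. Then MW = 0.9 × 0.5 + 0.1 × (1 − q) = 0.5 + 0.10 × (0.5 − q).

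- True worst rank, q = 0: 0.550
- b = 6: 0.5 + 0.10 × 0.496 = 0.550
- b = 4: 0.5 + 0.10 × 0.477 = 0.548
- b = 2: 0.5 + 0.10 × 0.409 = 0.541
- b = 0: 0.5 + 0.10 × 0.248 = 0.525

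At b = 0 the simulated MW is 0.501, 0.524 and 0.541 for mean changes of 0, +2 and +4. At b = 10 it does not differ from the true worst rank.

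**Step 5: can the rule be executed?** SAP section 4 records Stroop in seconds and Reaction Time as movement and reaction times. Neither document states a worst possible value for them. Trail Making has truncated variables at each visit, which implies a cap, but the limit is not given.

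**Step 6: means.** One HAM-A change of +41 among 30 patients adds 41/30 = 1.4 points to the arm mean compared with a change of zero. A median is far less sensitive to such a value.

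**The case against.** The strongest reply is that 13.12.3 is headed and introduced as a worst-rank rule, and that no section says the score is substituted before differencing. That is fair: the defect is an unstated order of operations as much as a wrong rule. The raw-scale reading is still the more natural one. The section speaks of the score of the outcome scale, LPCF in 13.12.4 is transformed back to the raw scale, and SAP section 4 holds raw visit values apart from the baseline differences.

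The entry criteria also make floor baselines less likely, since Protocol 6.1 requires a patient able to comply. This limits the number of patients affected but does not repair the rule.

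Four stronger readings may tempt a reader, and the documents do not support them.

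- That the most impaired patients generally outrank completers. Only those at or near the worst score at baseline do, and only over completers who declined by more than b.
- That half the signal is lost, from MW 0.550 to 0.525. Patients who become untestable had a baseline score and get −b. The half-loss needs all of them to start at the floor. Those already untestable at baseline are balanced by randomisation in expectation.
- That timed tests can have no worst score. The truncated Trail Making variables imply a cap, and 13.12.1 offers a route for unbounded scales.
- That the SAP gives code-2 patients LPCF or leaves them missing. The SAP is silent, and the protocol uses the same LPCF label alongside its worst-rank rule.

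Last, tying a patient who was untestable throughout below every observed decline treats stable severe impairment as the worst decline. That is a choice of what to estimate, and it has to be acknowledged.

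**Conclusion.** The concern holds in a limited form. The rule does not guarantee the worst rank on the analysed scale, and this follows from the text without assumptions. How often it fails depends on how many code-2 patients start near the worst score. Under the assumed MoCA changes, the share of completers outranked falls from about 25% at b = 0 to 9% at b = 2 and under 1% at b = 6. It is negligible for HAM-A at plausible baselines. The MW figures are for one component of nine under an assumed imbalance of 10% against none. The documents give no baseline distribution, floor frequency or code-2 rate, so the effect on the trial result cannot be stated.

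Three gaps do not depend on size: no stated worst value for Stroop or Reaction Time and no Trail Making limit, no action for code 2 in the SAP, and no code for death. This should be fixed before the SAP is final and the blind is broken, but nothing here shows that the primary result would be materially biased.

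**What to change.** In Protocol 13.12.3 and SAP 12.1, use the second option that Protocol 13.12.1 already allows, applied to the analysed change:

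- For each component and visit, give all code-2 patients one tied value worse than the worst observed change in the pooled arms. This also removes the need for a worst possible value on the timed tests.
- Apply the same principle to deaths, give them a code, and state whether they rank below or with code 2.
- State that this rule overrides LPCF for code 2.
- State the Trail Making truncation limit.
- Add medians and quartiles to SAP 12.2. The tied value is arbitrary, so means and standard deviations that include it have no clear meaning.

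The price is that a patient untestable at both visits is ranked below patients with an observed decline. Say so, and report a sensitivity analysis for patients untestable at baseline, for example ranking them at zero change. The cost is a few lines of text and one extra analysis, with no new data and no change in sample size.

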13.9. Sample Size Calculation

The power for this study is determined based on the following design specifications:

- (a) One-sided type I error defined as alpha = 0.05 (multiple level alpha, see section 13.7)
- (b) Type II error defined as $\beta = 0.2$ (Testpower 80%)
- (c) Design alternative effect size: Mann-Whitney statistic (MW) = 0.64 (medium-sized difference according to Cohen (Colditz, 1988); assuming a normal distribution the effect size MW may easily be re-expressed as the well-known Cohen effect size (Cohen, 1988) of a standardized difference (Cohen's d): MW = 0.64 means Cohen's d = 0.5)
- (d) Estimated correlations among the single outcome scales included in the global statistics $\rho = 0.4$)

Nonparametric sample size calculations within the framework of a multiple outcome approach (Wei-Lachin procedure- Wei and Lachin, 1984; Lachin 1992) was performed applying the validated software Nnpar 1.0 from idv Data Analysis and Study Planning, Krailling/Munich (see also Tang, 1989; Lachin, 1981). A good example for sample size calculation according to the Lachin approach (Wei and Lachin, 1984; Lachin 1992; Lachin, 1981) in multidimensional trials with neuroprotective agents is also given by Huang (2008).

Please note: further details of the effect size (Mann-Whitney statistic) are described in section 13.10, further details of sample size assessment are described in the separate document "Sample Size Assessment Based on a Multidimensional Efficacy Approach".

Based on the above design specifications, the total required sample size for the multivariate ensemble results in 30 patients per group (including 10% enhancement for usual "ambiguities", e.g., dropouts). With this sample size a "medium-sized" group difference (MW = 0.64) with regard to the multivariate outcome ensemble at month 3 and 6 can be detected with a power of 80%.

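### Worst-score replacement for code 2 is not confined to follow-up, so a patient untestable at baseline would be credited with an artificially large improvement

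*Protocol*

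**What the plan says.** - Protocol 13.12.2: "outcome scales will be coded for every patient and visit according to the following scheme". Code 1 is a valid result, code 2 is failure to complete for a neurological reason due to the injury, and code 3 is failure for another reason.
- Protocol 13.12.3, on code 2: "These missing data are replaced by the worst possible score of the corresponding outcome scale". It has no restriction by visit.
- Protocol 13.12.4, on code 3: the last percentile is carried forward only where an earlier follow-up evaluation exists; otherwise the scale stays missing. A code 3 at baseline is therefore left missing.
- Protocol 11.1 and SAP 7: all the scales are given at the Screening and Baseline Visit, then on days 101 and 180.
- Protocol 13.4.2, repeated in SAP 8.2.1 and 9: all nine ensemble items are changes from baseline, for example "Processing Speed Index, Changes from Baseline, LPCF, ITT".
- Protocol 13.13.3 and SAP 10: the ITT set requires a post-baseline observation but no observed baseline score.
- SAP 12.1 repeats the codes, including "2 = unable to complete (TBI-related neurological reason) [describe reason", but gives no replacement rule.

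**The concern.** Protocol 13.12.1 justifies worst-score replacement as protection against bias when the most impaired patients have no result. It works by ranking them last. Applied to a baseline value inside a change score, it does the reverse. The imputed starting point is the floor of the scale, so almost any later result looks like a large gain, and the most impaired patients move to the top of the ranking.

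These ranks would appear in both arms, at both follow-up visits and on every affected scale. They pull the Mann-Whitney effect towards 0.50, and they make the averaged statistic respond to how many such patients happen to fall in each arm. A programmer who followed 13.12.2 and 13.12.3 to the letter would create them.

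**Working it through.** **1. The plan's own figure (background; not disputed).** Inputs from Protocol 13.9: "One-sided type I error defined as alpha = 0.05", power 80%, "Mann-Whitney statistic (MW) = 0.64", "Estimated correlations among the single outcome scales included in the global statistics" of 0.4, and 30 per group "including 10% enhancement for usual" ambiguities such as dropout.
- One scale, Noether: n = (1.645 + 0.842)² / [6 × (0.64 − 0.5)²] = 52.57 per group.
- Averaging over k scales multiplies this by f = (1 + (k − 1) × 0.4)/k. For k = 9, f = 0.4667, n = 24.53, rounded up to 25; 25/0.9 gives 28 per group.
- The stated figure is 30. The k used is not given: k = 5 gives 31–32 and k = 18 gives 26. The plan's figure is thus reproduced to within two patients with k = 9.

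**2. Size of the artefact for one patient.**
- HAM-A (range 0 to 56, Protocol 9.1): baseline becomes 56. A follow-up of 25 gives 56 − 25 = 31 points of improvement. A tested patient with baseline b can improve by at most b, so nobody with baseline 30 or less can match it. HAM-A is clinician-rated; it is used here because its range is stated.
- MoCA (maximum 30, Protocol 9.1; minimum 0 is an assumption): baseline becomes 0, so a follow-up of 15 gives +15. A tested patient can gain at most 30 − b, so nobody with baseline above 15 can match it.
- Simulated MoCA ranks among 60 patients (assumed baseline mean 18–24, SD 3–5; gain 2–4, SD 3–4): a follow-up of 12 or more exceeds 98–100% of the others on average. A follow-up of 8 exceeds 84–99%.
- Still code 2 at follow-up: worst minus worst = 0. Under the same assumed gains this is the 25th percentile, Φ(−2/3), or the 16th, Φ(−4/4). That is not a large gain, but not the intended last rank either.

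**3. Dilution.** Suppose a share p of each arm takes the top ranks on a scale. If those patients show no treatment difference among themselves:

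MW′ = (1 − p)² × 0.64 + p(1 − p) + 0.5p²

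For p = 0.10: 0.5184 + 0.09 + 0.005 = 0.6134.

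Approximate power = Φ(√[6n(MW′ − 0.5)²/f] − 1.645), with n = 30 and f = 0.4333 (nine scales at two visits, all correlations taken as 0.4). In the last column those patients' changes are left missing instead: MW = 0.64 and n = 30(1 − p).

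| p (assumed) | MW′ | Power, baseline imputed | Power, change left missing |
|---|---|---|---|
| 0 | 0.640 | 0.887 | 0.887 |
| 5% | 0.626 | 0.824 | 0.872 |
| 10% | 0.613 | 0.747 | 0.856 |
| 20% | 0.590 | 0.572 | 0.818 |

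This table assumes that every scale is affected.

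**4. Fewer scales affected.** Simulation of the Wei-Lachin test: 27 per arm (30 less 10%), d = 0.5, correlation 0.4 between scales and 0.7 between visits on the same scale, 2,000–4,000 trials per setting. Affected patients take top ranks at both visits. Ranges cover separate runs, which differ by Monte Carlo error, variance estimator and the cross-visit, cross-scale correlation.
- No patient coded 2 at baseline: power 85–89%.
- 10% rate: 68–72% with all seven performance scales affected, 80% with four, 84% with two, 86% with one.
- 5% rate, seven scales: 78–80%.
- Type I error over all randomisations: about 5–6%.

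**5. Chance imbalance.** Two such patients against none, 30 per arm, no effect: MW = (28/30) × 0.5 + (2/30) × 1 = 0.533 on that scale. Conditional on 4 versus 1 (combined arm versus Cerebrolysin alone), simulated false positives are 16–18% with seven scales, 11% with four, 8% with two and 7% with one. Conditional on 1 versus 4, power is 36–37%, 67%, 80% and 82%. At a 10% rate and 27 per arm, an imbalance of three or more has probability 0.25, half of it (0.125) in the direction that inflates false positives. At a 5% rate these are 0.11 and 0.056.

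**The case against.** The strongest reply concerns intent and frequency. No section says that a baseline value is to be imputed. Protocol 13.12.1 motivates the rule by death and by inability to complete tests during the study, and 13.12.4 is framed around follow-up. Inclusion criteria (Protocol 6.1) require a patient able to meet the protocol's demands, and the baseline battery is one of them. SAP 7 places baseline around day 30, not in the acute phase. This stands in part: follow-up was probably what the authors had in mind, and such patients may be rare. But the criterion does not require completion of the baseline tests, and the text as written covers baseline.

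On size, the seven-scale case is an extreme, since it needs a patient untestable on every performance scale and then testable at both later visits. For the timed tests (Stroop, Trail Making, Reaction Time) neither document defines a worst possible score. SAP 4 lists truncated Trail Making times but no cap. A top rank there is assumed. The percentages also apply only to the protocol's Wei-Lachin test, not to the Kruskal-Wallis test with Dunn comparisons in the SAP's confirmatory section.

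A reader might infer that the trial's result would turn on where these patients fall and not on treatment, or that the primary test is biased. The documents do not support that. Code 2 at baseline is fixed before treatment, so randomisation balances it in expectation and overall type I error stays near 5%. The conditional error rates in step 5 describe particular unlucky allocations.

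**Conclusion.** The concern holds as a defect in a stated rule: worst-score replacement does not exclude baseline and, combined with change scores, gives the opposite of what it is meant to do. The consequence is dilution of the effect and sensitivity to chance imbalance, not systematic bias.

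The size cannot be established, because no rate for code 2 at baseline is given. Under the stated assumptions the loss of power at a 10% rate runs from about 17 percentage points (all seven performance scales) to little or none (one or two scales, 84–86% against 86–88% with none affected in the same run). At a 5% rate with seven scales, power is about 78–80%, close to the planned 80%. If no patient is coded 2 at baseline, nothing is lost. The case for acting rests on the clear reversal of purpose and the small cost of correction, not on a demonstrated large loss.

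**What to change.** In Protocol 13.12.3 and SAP 12.1:
- Restrict worst-score replacement to the efficacy evaluations on study days 101 and 180. Name the days, because Protocol 11.1 and SAP 7 call day 101 Visit 1 while the variable list in SAP 4 uses Visit 1 for baseline.
- Where a scale is code 2 at baseline, do not impute it; treat that patient's change on that scale as missing. A code 3 baseline is already left missing under Protocol 13.12.4.
- Report the number of such patients by arm and scale.

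These values are not missing completely at random, but the exclusion rests only on pre-treatment status, so the arms stay comparable. The result on that scale then describes patients who could be tested at baseline.

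The cost is a few sentences and a small programming change, to be settled before unblinding. The downside is that affected patients contribute nothing on those scales, including any who remain untestable later. In the closed-form model at a 10% rate, power is 0.856 with the change left missing, against 0.747 with the baseline imputed and 0.887 with no such patients.
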